9.2 Study completion and post-study treatment

Study completion is defined as when the last subject finishes his/her Follow-Up visit (study completion visit), and any repeat assessments associated with this visit have been documented and followed-up appropriately by the Investigator, or in the event of an early study termination decision, the date when the last patient completes his/her premature termination visit (see [Section 9.1.4](#)).

Upon completion of a patient's participation in the study, he/she should be treated according to his/her individual needs. It is not planned to provide QBW251 to study participants after the study is completed due to the early stage of development. Since this study is a Phase 2 study, the safety profile of the drug has not yet been established to the extent considered adequate for a provision of QBW251 with less stringent safety monitoring. Should there be patients with significant clinical benefit from QBW251 over approved treatment alternatives and the safety profile allow for treatment outside of the study, Novartis will consider to continue provision of the investigational treatment to these patients. Should there be a request from an investigator to provide post-trial treatment to a patient with evidence of significant clinical benefit from the use of QBW251 over the use of approved treatments, and the safety profile of the drug allow for treatment outside of the controlled environment of a study, Novartis will consider to continue providing the investigational treatment to this patient.

10 Safety monitoring and reporting

10.1 Definition of adverse events and reporting requirements

10.1.1 Adverse events

An adverse event (AE) is any untoward medical occurrence (e.g. any unfavorable and unintended sign [including abnormal laboratory findings], symptom or disease) in a subject or clinical investigation subject after providing written informed consent for participation in the study. Therefore, an AE may or may not be temporally or causally associated with the use of a medicinal (investigational) product. The investigator has the responsibility for managing the safety of individual subject and identifying adverse events. Novartis qualified medical personnel will be readily available to advise on trial related medical questions or problems.

The occurrence of adverse events must be sought by non-directive questioning of the subject at each visit during the study. Adverse events also may be detected when they are volunteered by the subject during or between visits or through physical examination findings, laboratory test findings, or other assessments.

Adverse events must be recorded in the Adverse Events eCRF under the signs, symptoms or diagnosis associated with them, accompanied by the following information (as far as possible) (if the event is serious refer to [Section 10.1.2](#)):

1. The severity grade:
 - a. mild: usually transient in nature and generally not interfering with normal activities,
 - b. moderate: sufficiently discomforting to interfere with normal activities,
 - c. severe: prevents normal activities.
2. its relationship to the study treatment. If the event is due to lack of efficacy or progression of underlying illness (i.e. progression of the study indication) the assessment of causality will usually be 'Not suspected'. The rationale for this guidance is that the symptoms of a lack of efficacy or progression of underlying illness are not caused by the trial drug, they happen in spite of its administration and/or both lack of efficacy and progression of underlying disease can only be evaluated meaningfully by an analysis of cohorts, not on a single subject.
3. its duration (start and end dates) or if the event is ongoing, an outcome of not recovered/not resolved must be reported.
4. whether it constitutes a SAE (see [Section 10.1.2](#) for definition of SAE) and which seriousness criteria have been met.
5. action taken regarding with study treatment.

All adverse events must be treated appropriately. Treatment may include one or more of the following:

- a. Dose not changed,
 - b. Dose Reduced/increased,
 - c. Drug interrupted/withdrawn.
6. its outcome
 - a. not recovered/not resolved,
 - b. recovered/resolved,
 - c. recovering/resolving,
 - d. recovered/resolved with sequelae,
 - e. fatal, or
 - f. unknown.

Conditions that were already present at the time of informed consent should be recorded in medical history of the subject.

Adverse events (including lab abnormalities that constitute AEs) should be described using a diagnosis whenever possible, rather than individual underlying signs and symptoms.

Adverse event monitoring should be continued for at least 30 days following the last dose of study treatment.

Once an adverse event is detected, it must be followed until its resolution or until it is judged to be permanent (e.g. Continuing at the end of the clinical trial), and assessment must be made at each visit (or more frequently, if necessary) of any changes in severity, the suspected relationship to the interventions required to treat it, and the outcome.

Information about adverse drug reactions for the investigational drug can be found in the Investigator's Brochure (IB).

Abnormal laboratory values or test results constitute adverse events only if they fulfill at least one of the following criteria:

- they induce clinical signs or symptoms
- they are considered clinically significant
- they require therapy

Clinically significant abnormal laboratory values or test results must be identified through a review of values outside of normal ranges/clinically notable ranges, significant changes from baseline or the previous visit, or values which are considered to be non-typical in subjects with the underlying disease. Alert ranges for laboratory and other test abnormalities are included in [Section 16.1](#).

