Clinical monitoring includes the use of an electronic diary with the EXACT questionnaire to enable daily symptoms assessment, as well as safety assessments during visit days at the investigational site. These include a careful assessment of adverse events, as well as triplicate ECGs, hematologic and clinical chemistry laboratory assessments, urinalysis and vital signs measurements. As a formal thorough QT assessment of QBW251 has not been completed, triplicate ECGs pre- and post-dose (at the time to reach maximum (peak) plasma concentration following drug administration (T_{max})) will be performed at Day 1, at Day 15 (when all patients have reached steady state concentration of the investigational drug), and at Day 169 (end of treatment). These assessments will be complemented by the corresponding PK sampling (trough and C_{max}). The PK sampling is also part of a more granular PK monitoring (detailed in schedule of assessment [Table 8-1](#)), which has been put in place to ensure that patient exposures are in general consistent with a threshold (area under the plasma concentration curve over 24 hours (AUC_{0-24h}) = 91 700 ng×h/mL) that was established based on animal (monkey) data. As this threshold represents an average of the exposures observed in those animals after 39 weeks of treatment with QBW251, this limit is not absolute and few patients are expected to exceed it. In prior QBW251 studies, patients with exposures above this threshold reported either no adverse events or mild to moderate ones.

In addition to the sampling described above, the PK monitoring plan will generate C_{min} data at all visits and additional PK samples are requested to be taken in case of treatment-emergent serious adverse events. Study drug discontinuation and cohort stopping rules related to exposure have been introduced into the protocol as well (see [Section 9.1.4.1](#))

Finally a sub-group of approximately 48 patients will undergo serial PK assessments to further characterize the PK profile of QBW251 before transitioning into the confirmatory Phase 3.

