Visit Name	Screening	Run-In 1	Run-In 2	Day 1	Week 2	Week 4	Week 8	Week 12	Week 16	Week 20	Week 24	PSW ¹	Follow-Up	Unscheduled
Days	-21	-14	1	1	15	29	57	85	113	141	169	-	197	-
Informed consent	X													
Demography	X													
Physical Examination	X										X	X		
Body Height	X													
Body Weight	X										X	X		
Vital Signs	X	X	X	(X) ⁵	X	X	X	X	X	X	X	X	X	
Medical history/current medical conditions ²	X													
COPD exacerbation history	X													
Smoking history	X													
Smoking status	(X) ³										X	X		
Inclusion/Exclusion criteria	X	X	X											
Concomitant medications	X	X	X	X	X	X	X	X	X	X	X	X	X	
Dispensation of rescue medication	X	X		X		X	X	X	X	X	X			
Dispensation of standard background triple therapy		X		X		X	X	X	X	X	X			
Dispensation of study drug				X		X	X	X	X	X				
Spirometry		X		X		X	X	X	X	X	X	X	X	
Spirometry Reversibility Test		X												

Period	Screening	Run-In		Treatment									Follow-Up	Unscheduled
Visit Name	Screening	Run-In 1	Run-In 2	Day 1	Week 2	Week 4	Week 8	Week 12	Week 16	Week 20	Week 24	PSW ¹	Follow-Up	Unscheduled
Days	-21	-14	1	1	15	29	57	85	113	141	169	-	197	-
Electrocardiogram (ECG) ⁴		X	X	X ⁵	X ⁶	X	X	X	X	X	X ⁶	X	X	
COPD Assessment Test (CAT) ⁷		X												
St. George's Respiratory Questionnaire ⁷			X					X			X	X		
Patients Global Impression of Severity Scale (PGI-S general question) ⁷			X					X			X	X		
Patients Global Impression of Severity Scale (PGI-S specific question) ⁷			X					X			X	X		
Cough And Sputum Assessment Questionnaire (CASA-Q) ⁷			X					X			X	X		
e-Diary - rescue medication use	from Day -21	X	X	X	X	X	X	X	X	X	until Day 169	until PSW		
e-Diary - EXACT Questionnaire ⁸		from Day -14	X	X	X	X	X	X	X	X	until Day 169	until PSW		

[figure not shown]

Period	Screening	Run-In		Treatment									Follow-Up	Unscheduled
Visit Name	Screening	Run-In 1	Run-In 2	Day 1	Week 2	Week 4	Week 8	Week 12	Week 16	Week 20	Week 24	PSW ¹	Follow-Up	Unscheduled
Days	-21	-14	1	1	15	29	57	85	113	141	169	-	197	-
Assessment of childbearing potential	S													
Pregnancy Test (serum) ¹⁰		X												
Pregnancy Test (urine) ¹⁰	X		X			X	X	X	X	X	X	X	X	
Hematology		X		X		X	X	X	X	X	X	X	X	
Clinical Chemistry ¹¹		X		X		X	X	X	X	X	X	X	X	
Urinalysis ¹²		X	X			X	X	X	X	X	X	X	X	
PK blood collection				X ¹³	X ¹³	X	X	X	X	X	X ¹³	X		X ¹⁴
PK Sub-group (serial PK sampling)				X ¹⁵	X ¹⁵									
Adverse Events	X	X	X	X	X	X	X	X	X	X	X	X	X	
Serious Adverse Events	X	X	X	X	X	X	X	X	X	X	X	X	X	

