Surgeries & procedures review	X	X	X	X	X	X	X	X	X	X	X	X	X	
Contact IVRS/IWRS	X	X	X ¹⁶	X	X	X	X	X	X	X	X	X	X	
Study Disposition Page	X ¹⁷		X ¹⁸								X ¹⁹	X ¹⁹	X ²⁰	
Study completion information												X ²¹	X	

[figure not shown]

Table 8-2 Timed assessments for all visits

	Time Point ¹	PROs at site	Urine Sample	ECG	Vital Signs ³	Hemato-logy/ Blood Chemis-try	Spiro-metry ⁴	PK Blood Samp-ling
Day 1	Prior to -45 min	X						
			X	X ²	X			
	Prior to -45 min	Randomization						
	-45 min						X	
	-45 to -20 min approximately					X		X
	-15 min						X	
	0	Study drug administered in clinic						
3 h				X ²				X
Week 2	Prior to Study drug			X ²	X			
	Prior to Study drug							X
	0	Study drug administered in clinic						
	3 h			X ²				
Week 4	Prior to -45 min			X ²	X			
	-45 min						X	
	-45 to -20 min approximately					X		X
	-15 min						X	
	0	Study drug administered in clinic						
Week 8	Prior to -45 min			X ²	X			
	-45 min						X	
	-45 to -20 min approximately					X		X
	-15 min						X	
	0	Study drug administered in clinic						

	Time Point ¹	PROs at site	Urine Sample	ECG	Vital Signs ³	Hemato-logy/ Blood Chemis-try	Spiro-metry ⁴	PK Blood Samp-ling
Week 12	Prior to -45 min	X						
	Prior to -45 min			X ²	X			
	-45 min						X	
	-45 to -20 min approximately					X		X
	-15 min						X	
	0	Study drug administered in clinic						
Week 16	Prior to -45 min			X ²	X			
	-45 min						X	
	-45 to -20 min approximately					X		X
	-15 min						X	
	0	Study drug administered in clinic						
Week 20	Prior to -45 min			X ²	X			
	-45 min						X	
	-45 to -20 min approximately					X		X
	-15 min						X	
	0	Study drug administered in clinic						
Week 24	Prior to -45 min	X						
			X	X ²	X			
	-45 min						X	
	-45 to -20 min approximately					X		X
	-15 min						X	
	0	Study drug administered in clinic						
	3 h			X ²				X
PSW	Prior to -45 min	X						
			X	X ²	X			

	Time Point ¹	PROs at site	Urine Sample	ECG	Vital Signs ³	Hemato-logy/ Blood Chemis-try	Spiro-metry ⁴	PK Blood Samp-ling
	-45 min						X	
	-45 to -20 min approximately					X		X
	-15 min						X	
	0	Theoretical study drug timepoint						
	3 h							

¹ Time relates to the dose given from spirometry device at visit unless otherwise specified.

² Triplicate ECG measurements required.

³ Systolic/diastolic blood pressure and heart rate.

⁴ A minimum 3 minutes rest period from the beginning of ECG assessments to the start of spirometry maneuvers must be observed at all times.

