10.1.3 SAE reporting

To ensure subject safety, every SAE, regardless of causality, occurring after the subject has provided informed consent and until 30 days following the last administration of study treatment if there are post-treatment Follow-Up visits with no required procedures must be reported to Novartis safety within 24 hours of learning of its occurrence. Detailed instructions regarding the submission process and requirements are to be found in the investigator folder provided to each site.

SAEs occurring after the subject has provided informed consent until the time the subject is deemed a screen failure or run-in failure must be reported to Novartis.

[figure not shown]
For randomized subjects, SAEs occurring after the subject has provided informed consent until 30 days after the subject has discontinued or stopped study treatment (which usually would be the time of the Follow-Up visit) must be reported to Novartis.

All follow-up information for the SAE including information on complications, progression of the initial SAE and recurrent episodes must be reported as follow-up to the original episode within 24 hours of the investigator receiving the follow-up information. An SAE occurring at a different time interval or otherwise considered completely unrelated to a previously reported one must be reported separately as a new event.

If the SAE is not previously documented in the Investigator’s Brochure or Package Insert (new occurrence) and is thought to be related to the study treatment, a Novartis Chief Medical Office and Patient Safety (CMO & PS) department associate may urgently require further information from the investigator for health authority reporting. Novartis may need to issue an Investigator Notification (IN) to inform all investigators involved in any study with the same study treatment that this SAE has been reported.

Suspected Unexpected Serious Adverse Reactions (SUSARs) will be collected and reported to the competent authorities and relevant ethics committees in accordance with EU Guidance 2011/C 172/01 or as per national regulatory requirements in participating countries.

Any SAEs experienced after the 30 day period from the last treatment (usually marked by the Follow-Up visit) should only be reported to Novartis Safety if the investigator suspects a causal relationship to study treatment.

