2.8.1 Adverse events (AEs)

The on-treatment period for adverse events lasts from the date of first administration of double-blind study treatment to 30 days after the date of the last actual administration of double-blind

study treatment. Adverse events will be summarized by treatment group. Summary tables for AEs will summarize only on-treatment events (also known as treatment-emergent AEs).

The number (and percentage) of subjects with treatment-emergent adverse events will be summarized in the following ways:

- by treatment and preferred term (PT).
- by treatment, primary system organ class (SOC) and PT.
- by treatment, SOC, PT and maximum severity.

Separate summaries by SOC and PT will be provided for:

- AEs suspected to be study medication related
- fatal AEs
- leading to treatment discontinuation
- leading to dose interruptions and/or adjustments
- serious adverse events (SAEs)

Further SAEs will be summarized by PT.

In addition, treatment emergent AEs and SAEs will be presented by treatment, system organ class and preferred term, showing exposure adjusted event rates (i.e., the number of events expressed in rates per 100 patient years).

Unless otherwise specified, SOCs will be sorted alphabetically and, within each SOC, the PTs will be sorted in descending order of frequency in the highest QBW251 dose. A subject with multiple adverse events within a SOC or PT is only counted once towards the total of the SOC or PT.

Listings will be provided for all AEs, SAEs and fatal AEs.

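### The post-dose adverse-event window is 30 days, but the last scheduled contact falls 28 days after a completer's last investigational dose

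*Protocol*

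**What the plan says.** **The window.** Protocol 10.1.1: "Adverse event monitoring should be continued for at least 30 days following the last dose of study treatment". For randomised patients, protocol 10.1.3 requires SAE reporting "until 30 days after the subject has discontinued or stopped study treatment (which usually would be the time of the Follow-Up visit"; a later sentence in 10.1.3 again ties the 30-day point to that visit. For analysis, SAP 2.8.1 runs the on-treatment period from first administration "to 30 days after the date of the last actual administration of double-blind" study treatment. Protocol 12.5.2 and SAP 2.1.1.3 use the same 30 days.

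**How events are found.** Protocol 10.1.1: "The occurrence of adverse events must be sought by non-directive questioning of the subject at each visit during the study". It adds a second route: "Adverse events also may be detected when they are volunteered by the subject during or between visits".

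**The schedule.** The day row of Table 8-1 reads "Days -21 -14 1 1 15 29 57 85 113 141 169 - 197"; the last two dated visits are Week 24 (Day 169) and Follow-Up (Day 197). SAP 5.2 also lists Follow-Up at Day 197. Protocol 4.5 schedules ECGs "and at Day 169 (end of treatment"). At Week 24, Table 8-2 has "Study drug administered in clinic" at time 0, with a 3-hour ECG and PK sample. The study-drug dispensing row of Table 8-1 ends at Week 20.

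**The concern.** The protocol sets a minimum period of adverse-event monitoring after the last dose and treats the Follow-Up visit as marking its end. On the planned days, that visit comes before the period is over. A site that keeps exactly to the schedule, and relies on the remark in 10.1.3, could close a completer at 28 days believing that the 30-day requirement had been met.

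What is at stake is the completeness of treatment-emergent event counts and exposure-adjusted rates at the very end of the window, mainly for non-serious events. The window used in the analysis extends slightly beyond the period in which patients are actively questioned.

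**Working it through.** **Inputs**
- Last double-blind dose of an on-schedule completer: Day 169 (Table 8-2, Week 24; protocol 4.5; no study drug dispensed that day in Table 8-1).
- Last scheduled contact: Follow-Up, Day 197 (Table 8-1; SAP 5.2).
- Post-dose window: 30 days (protocol 10.1.1, 10.1.3, 12.5.2; SAP 2.1.1.3, 2.8.1).

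**Is Day 197 a reading error?** No. The plan's own total can be reproduced from it. Screening is on Day -21 and there is no Day 0 (SAP 2.1.1.1), so the span to Day 197 is 197 + 21 - 1 = 217 days, and 217 / 7 = 31.0 weeks. The protocol summary states 31 weeks. Treatment is (169 - 1) / 7 = 24.0 weeks, and follow-up is (197 - 169) / 7 = 4.0 weeks, which fits the Weeks 25 to 28 given in protocol section 3.

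**The gap**
- Scheduled follow-up after the last dose: 197 - 169 = 28 days.
- End of the 30-day window: 169 + 30 = Day 199.
- Days with no scheduled contact: 199 - 197 = 2 (Days 198 and 199).
- Share of the post-dose period: 2 / 30 = 6.7%.
- Share of the whole on-treatment adverse-event window, Days 1 to 199: 2 / 199 = 1.0%.

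**Sensitivity to the actual dates**

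| Last dose | Follow-Up held | Days without scheduled contact |
|---|---|---|
| Day 169 | Day 195 | 4 |
| Day 169 | Day 197 | 2 |
| Day 169 | Day 199 or later | 0 |
| Day 168 | Day 197 | 1 |

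**Is a later contact planned elsewhere?** In Table 8-1 the AE and SAE rows end at Follow-Up and carry no footnote marker. The footnote texts are missing from the available copy, so this rests on the table body.

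**Which last dose?** The calculation takes the last dose to be that of the investigational drug, as SAP 2.1.1.3 and 2.8.1 do. Protocol 10.1.1 says study treatment, and the glossary and protocol 6.1 include background therapy in that term. Background therapy continues until Follow-Up (protocol 6.1.4). Read literally, the 30 days in 10.1.1 would run to 197 + 30 = Day 227.

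**The case against.** The strongest reply is that nothing prevents a site from meeting both texts. The duty in 10.1.1 stands on its own and is not tied to a visit. SAEs must be reported to 30 days whatever the visit date, and causally suspected SAEs after that. Patients may volunteer events between visits. Section 8 asks for visits near the planned day but sets no numeric tolerance, and SAP 5.2 assigns anything from Day 184 onward to Follow-Up, so a late visit would close the gap. The word usually in 10.1.3 signals an approximation. With a single-dose half-life of 10 to 16 hours (protocol 4.2), five half-lives are 50 to 80 hours, so days 29 and 30 lie long after exposure.

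Much of this stands, and it rules out several stronger readings:
- A reader might infer that these two days are never asked about, or that the 30-day window is not delivered. The documents support only that no questioning is scheduled for them when Follow-Up is on Day 197.
- A reader might put the affected share at about 80% of patients, from the 20% dropout in protocol 12.8. That figure is a power assumption with no stated time horizon. The documents give no Week 24 completion rate and no proportion attending exactly on Day 197.
- A reader might infer biased ascertainment, because patients who stop drug early and keep attending (protocol 9.1.1) can be questioned across the full 30 days. The nominal schedule is the same in every arm, and the documents give nothing from which to quantify a difference between arms.
- A reader might attribute the link between 30 days and Follow-Up to both safety sections. Only 10.1.3 makes it, and only for SAEs.

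None of this removes the mismatch. Attending on the planned day produces the shortfall, volunteered reports supplement questioning at visits but do not replace it, and the SAE duty does not cover non-serious events and depends on the site learning of the event.

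**Conclusion.** This is a real but minor internal inconsistency. The stated 30-day window and the planned last contact differ by 2 days for an on-schedule completer, and the remark in 10.1.3 that the 30-day point usually coincides with Follow-Up does not match the schedule. The size is 2 of 30 post-dose days, or about 1% of the 199-day adverse-event window. No efficacy result is touched, and no safety conclusion is shown to change.

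The conclusion assumes a last investigational dose on Day 169, Follow-Up on Day 197, and no later contact hidden in the missing footnotes. It also assumes that last dose means the investigational drug. The wider Day 227 reading of 10.1.1 follows from the defined term, but both documents tie the adverse-event analysis window to double-blind or randomised treatment. It therefore shows that the term needs clarifying and does not support claiming a longer gap in the on-treatment window.

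**What to change.** Reconcile protocol 10.1.1, 10.1.3 and 12.5.2 and SAP 2.1.1.3 and 2.8.1 with the Day 197 Follow-Up visit in Table 8-1 and SAP 5.2, so that the last planned adverse-event contact and the stated post-dose AE and SAE window agree. Correct the two remarks in 10.1.3 that equate the 30-day point with Follow-Up if they remain untrue after that. State in 10.1.1 whether the window runs from the last dose of investigational drug or from the last dose of any study treatment as the glossary defines it. Which text gives way is for the sponsor to decide.

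The cost is small: wording changes in a few sections. If the sponsor changes the schedule itself, the follow-up description in protocol section 3, the 31-week participation figure and SAP 5.2 would need to follow.
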